3.2 Secondary objectives

To identify factors impacting on quality indicators e.g., number of sets, contamination, time to microbiology lab analyser; whether blood culture sampling occurs prior to administration of antibiotic.

To conduct a secondary analysis to assess extent to which availability of blood samples was associated with changes to antibiotic choice at antibiotic review.

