3.3 Outcome measures/endpoints

3.4 Primary endpoint/outcome

Primary outcome measure is occurrence of blood culture sampling. In line with Shallcross (2016) (18) we define blood culture sampling as a request for a blood culture recorded in hospital records within 48 hours of patient arrival at ED (Y/N)

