3.5 Secondary endpoints/outcomes

Quality indicators (e.g., number of sets, contamination, time to microbiology lab analyser; whether blood culture sampling occurs prior to administration of antibiotic.)

Changes to antibiotic choice at antibiotic review.

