6.3 Source Data

Analysis will identify situational/contextual predictors of reliable blood culture sampling. We have specified a minimum set of measures, identified in agreement with the three participating hospitals based on routine data that is collected and could be made available from all three hospitals. This will be developed into a fully-specified data extraction schedule with input from our expert advisory group (e.g. listing the broad spectrum antibiotic that are of interest), tailored for each hospital to reflect variations in the way their data are coded. This will include the following measures:

- Date & time of arrival in ED/admissions unit
- Antibiotics patient is already taking prior to admission where applicable
- Location antibiotic prescribed (ED, AMU etc)
- Type of antibiotic prescribed
- · Date and time antibiotic prescribed
- Dates and times of antibiotic administration
- Documented microbiology results
- Changes to antibiotic schedule
- Patient demographics (IMD based on postcode, year of birth, ethnicity, gender)
- Patient severity (NEWS score)
- Recorded diagnosis at admission and at discharge

Where available we will also collect data on quality indicators as secondary outcomes:

e.g., number of sets of blood culture bottles filled (guidelines recommend 2 sets of two bottles), contamination of sample, time to microbiology lab analyser

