7 STATISTICS AND DATA ANALYSIS

Data analysis:

Descriptive statistics will be used to summarise the frequency and distribution of timing of blood culture ordering. We will also produce histograms or box plots to visualise the distribution of these measures. Logistic regression will be used to assess covariates associated with the probability of blood culture being ordered within 48 hours of admission (binary yes/no outcome). Relevant covariates to be assessed include situational/contextual factors, patients demographics, and patient outcomes.

To identify factors impacting on quality indicators e.g., number of sets, contamination, time to microbiology lab analyser; whether blood culture sampling occurs prior to administration of antibiotic, appropriate methods will be used depending on the data type of the quality indicator. Continuous variables will be assessed via linear regression, and binary quality indicators by logistic regression.

A final analysis to investigate the extent to which availability of blood samples was associated with changes to antibiotic choice at antibiotic review will be assessed again using logistic regression (with yes/no antibiotic changed as the dependent variable, and yes/no blood sample available as the independent.

All models will be fully adjusted for covariates such as patient age, and will be mixed effects to account for the clustering effect of hospital, as data is being drawn from three sites. We will conduct sensitivity analyses to test the robustness of our results to different assumptions and model specifications. This will help to assess the reliability of our findings and identify potential sources of bias. We will carefully consider the strengths and limitations of each method and choose the most appropriate approach for each research question.

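### The antibiotic-change model does not say when a blood sample counts as available or who is at risk at review, so its odds ratio can exceed 1 with no true effect

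*Protocol*

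**What the plan says.** Protocol Part 1a, section 3.2 sets a secondary objective: the extent to which "availability of blood samples was associated with changes to antibiotic choice at antibiotic review". Section 3.5 gives the outcome as "Changes to antibiotic choice at antibiotic review", with no review time or window.

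Section 7 fixes the model as a logistic regression "with yes/no antibiotic changed as the dependent variable, and yes/no blood sample available as the independent". On adjustment it says "All models will be fully adjusted for covariates such as patient age, and will be mixed effects", the random effect being for hospital. Time at risk, early discharge and death are not mentioned. Sensitivity analyses are promised in general terms, and none is named for the order of events or early exit.

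The only dated definition of sampling is in section 3.4, for the primary outcome: a recorded request "within 48 hours of patient arrival at ED". Nothing says that this also defines the exposure here.

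The minimum data list in section 6.3 includes "Dates and times of antibiotic administration", "Changes to antibiotic schedule" and documented microbiology results. It names no time for a result being reported, for a review, or for discharge or death.

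**The concern.** A yes/no regression of one in-hospital event on another is sound only if three things are fixed: the moment at which exposure is judged, the rule that exposure comes before outcome, and the patients who can still have the outcome at that moment. Section 7 fixes none of them.

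Two mechanisms follow.

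- **Early exit.** A patient who leaves or dies early has little time to be sampled or to have a change recorded, and can land in the no/no cell. Filling that cell raises the odds ratio.
- **Reversed order.** A sample or result that arrives after the change, possibly because of it, can count as exposure.

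At stake is the only quantitative model in the project that addresses whether sampling goes with altered antibiotic choice. Section 1 of Part 1a explains the value of cultures by their informing review of the first prescription. That mechanism needs information in hand at review, so an odds ratio produced by time in hospital would answer a different question.

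**Working it through.** The protocol gives no alpha, power, change rate or effect size for this analysis, so there is no figure to reproduce. The check asks what the model returns when sampling has no effect on change (true odds ratio 1).

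**1. Early exit, in closed form.** Let a fraction e leave before either event can happen. Among the rest, a fraction p are sampled and a fraction c are changed, independently. The cells are:

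- sampled and changed: (1−e)pc
- sampled, unchanged: (1−e)p(1−c)
- unsampled, changed: (1−e)(1−p)c
- unsampled, unchanged: (1−e)(1−p)(1−c) + e

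Hence OR = 1 + e / [(1−e)(1−p)(1−c)].

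Take p = 0.5 (Part 1a, section 1 reports that about half are not sampled) and c = 0.4 (assumed). The values of e are also assumed.

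- e = 0: OR = 1.00
- e = 0.02: 1 + 0.02/(0.98 × 0.5 × 0.6) = 1 + 0.02/0.294 = 1.07
- e = 0.05: 1 + 0.05/0.285 = 1.18
- e = 0.10: 1 + 0.10/0.270 = 1.37

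**2. Reversed order, in closed form.** Suppose half are sampled regardless, and a change prompts a sample in a fraction q of the unsampled. The odds of sampling are (0.5 + 0.5q)/(0.5 − 0.5q) among changers and 1 among the rest, so OR = (1+q)/(1−q).

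- q = 0.1: 1.1/0.9 = 1.22
- q = 0.2: 1.2/0.8 = 1.50
- q = 0.3: 1.3/0.7 = 1.86

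Simulation gave 1.21, 1.49 and 1.83. Counting only samples taken before the change gave 0.99.

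**3. Both mechanisms over time, by simulation** (400,000 patients per scenario, crude odds ratios, independent sampling and change). Apart from the 50% sampled, all inputs are assumptions: median time to exit 48, 96 or 168 h after a 6 h minimum; median request time 6 h (early) or 24 h (spread); result 36–72 h after sampling; and either a change at any time (median 36 or 72 h) or a change only at a review at 24–72 h (40% changed).

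| Reading of available | Outcome | Null OR |
|---|---|---|
| Request within 48 h, early requests | change at any time | 1.10–1.18 |
| Request within 48 h, early or spread requests | change only at review | 1.01–1.60 |
| Any sample in the stay, spread requests | change at any time | 1.6–2.0 |
| Result at any time in the stay | change only at review | 1.3–3.4 |
| Result at any time in the stay, early requests | change at any time | 2.8–5.1 |

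In the last row, 53–79% of exposed changers had changed before their result arrived.

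The minimum stay matters. Raising it from 6 h to 24 h brings the early-request reading to between 1.00 and 1.06. The result-at-any-time reading still gives about 1.3 to 4.4 over the two outcome definitions.

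**4. The remedy under the same inputs.** Restricting to patients in hospital and unchanged at a landmark, with exposure dated by then, gives 0.98–1.02 for a sample by 48 h and 0.98–1.02 for a result by 72 h. A further result-based run at 72 h gave 0.96–1.01. Restricting to patients in hospital at review, with the request before review, gives 0.99–1.01.

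**The case against.** The strongest reply is that the analysis is limited to change at antibiotic review. On that wording a change before review is not the outcome, and a patient who left before review was never eligible. This stands in part. A reader might infer that both variables run over the whole stay, but the text does not say so, and the review wording does order events to some degree. It is not sufficient: with the outcome confined to review in the simulation, the null odds ratio still exceeds 1 when patients gone before review are counted as unchanged. Nothing in the protocol says to exclude them.

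A second reply concerns size. A reader might carry the 48-hour rule over from the primary outcome and still quote the largest odds ratios. The rule is not stated for this exposure, and under it the bias is modest. With early requests and few exits in the first 24 hours it is close to nothing. The odds ratios above are also crude, while section 7 specifies adjusted mixed models and severity score is collected.

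Third, section 6.2 refers to a statistical analysis plan, section 6.3 calls its list a minimum to be developed into a full extraction schedule, and section 8.1.1 says that schedule will give definitions. Windows and at-risk sets are often left to such documents. That is fair, but the protocol already fixes the form of the model, and an analysis plan cannot use fields that were not extracted. Data are anonymised at the three trusts before transfer, so a missing field means going back to each.

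Fourth, order and administration times are already planned, so a dated exposure and an approximate change time can largely be recovered. This is correct and lowers the cost of the remedy.

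**Conclusion.** The point holds as a weakness in a specified secondary analysis. Run as section 7 describes it, the model can return an odds ratio above 1 when sampling has no effect, because available has no definition or time, need not precede the change, and has no at-risk set.

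The size is conditional. The null odds ratio is about 1.0 to 1.6 for a request within 48 hours. It is about 1.3 to 4.4 for a result at any time in the stay, with some settings reaching 5.1, so 4.4 is not a ceiling. Both ranges rest on assumed stay, request, change and result times that the documents do not give.

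A reader might infer that a spurious association is certain. The documents do not support that: the bias may be negligible if sampling is early and early exits are rare. No figure in the protocol is wrong, the primary outcome is untouched, and the objective is worded as an association.

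**What to change.** In Part 1a, section 7, anchor this analysis at the recorded antibiotic review or, where none is recorded, at a fixed landmark time stated in advance. Then:

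- include only patients still in hospital and on the initial antibiotic at that time;
- count as exposed only those whose culture was available by then, saying whether that means requested or collected, with a culture result reported by then as a stated alternative;
- count only changes at or after that time;
- vary the landmark as a sensitivity analysis.

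Add result-reported, review and discharge or death times to the extraction schedule under section 6.3. Order and administration times need no new request.

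The cost is a few timestamp fields from three sites and a short rewording. Patients who leave, die or change before the landmark drop out of this secondary analysis, so the estimate applies to those still on the initial antibiotic at that point. Their number should be reported by site.

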3 OBJECTIVES AND OUTCOME MEASURES/ENDPOINTS

3.1 Primary objective

To identify rate of occurrence and situational factors that affect whether blood culture sampling occurs, when broad-spectrum antibiotics for intravenous administration are prescribed within 24 hours of patient admission from emergency departments (ED).

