10.3 PUBLIC AND PATIENT INVOLVEMENT

Acceptability and Design

We convened a PPI group (Oct 2022) comprising six patients with experience of severe infection and hospital care to advise on study design (2F, 4M; 5 White British, 1 Asian). Group members were recruited from existing local PPI groups, and through informal contacts by the local Research Design Service PPI lead. The PPI engagement event took place online to enable participation from PPIE members who were unable to travel. The meeting consisted of a project presentation, where we presented our research questions and ideas for study design and methods.

Following the presentation, we invited an open discussion, allowing PPI group members to comment on all aspects of the presentation. PPI members were provided with a series of questions about study value and study design, and how we could involve patients in research, co-design, and dissemination. These were discussed during the meeting, and also sent to participants by email following the meeting inviting further feedback. In addition a further focused discussion was held online between [name] (PI) and [name] (PPI co-applicant). PPI feedback included the importance of considering patients from whom it is difficult to take blood, and for studying inequalities in blood sampling across patient groups, suggestions for patient involvement and the potential for patient-facing interventions, and dissemination suggestions. All feedback was taken into account in preparing this application. This includes:

- ensuring PPI representatives are involved in study team meetings
- providing training to all PPI members on research methods and on specific topics e.g. sepsis, antimicrobial resistance
- involving PPI members in analysis of qualitative data and in giving presentations of the findings
- producing Plain English summaries and a video about findings aimed at the public
- ensuring that patients are fully involved in the co-design process and consider the potential for a patient held/led intervention
- paying costs for PPI member conference attendance.

Undertaking, analysing and disseminating the research

- Research methods training and training on the clinical context will be provided to the PPI participants. Training will take place in year 1, and include online research methods training, and additional bespoke training in specific topics e.g. sepsis and antimicrobial resistance.

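### Part 1a's blanket full-adjustment rule mixes upstream factors, later steps and patient outcomes, so it is unclear whether the odds ratios for ethnicity, deprivation, gender and arrival time describe the overall gap in sampling

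*Protocol*

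**What the plan says.** The Part 1a primary objective (section 3.1) is "To identify rate of occurrence and situational factors that affect whether blood culture sampling occurs". Section 6.3 puts the aim as prediction: "Analysis will identify situational/contextual predictors of reliable blood culture sampling". It then lists the measures to be extracted. These include arrival date and time, deprivation, ethnicity, gender, NEWS and admission diagnosis, and also "Location antibiotic prescribed (ED, AMU etc", with the type of antibiotic and the time it was prescribed.

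Section 7 gives the primary model: "Logistic regression will be used to assess covariates associated with the probability of blood culture being ordered within 48 hours of admission". Its covariate classes are: "Relevant covariates to be assessed include situational/contextual factors, patients demographics, and patient outcomes". One rule then covers every Part 1a model: "All models will be fully adjusted for covariates such as patient age", with mixed effects for hospital. Age is the only individual covariate named in section 7.

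Section 10.3 records that patient contributors raised the importance of considering patients who are hard to bleed and "for studying inequalities in blood sampling across patient groups". It says all feedback was taken into account.

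Section 7 also promises unnamed sensitivity analyses on model specification and a method suited to each research question. Section 6.2 refers to a statistical analysis plan, which is not at hand.

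**The concern.** The measures in section 6.3 have a rough order in time. Demographics come first, then arrival. Where, when and with what the antibiotic was prescribed come later. Patient outcomes come after the culture has or has not been requested.

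A coefficient from a model holding all of these describes an early factor among patients already alike on the later steps. For ethnicity, that is the difference among patients prescribed in the same place at the same time. It is not the difference in sampling that patient groups experience. An objective worded as what affects sampling, and a recorded interest in inequalities, both point to the overall difference, at least alongside the adjusted one.

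Patient outcomes are the clearest problem on the text. They cannot influence an earlier decision to order a culture, and sampling may influence them. Conditioning on them has no clear use for this question and can distort the other coefficients.

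Part 1a findings feed the co-design workshops (Part 1c and Part 2 protocol, section 6.2). A factor that acts through place of prescribing could be misjudged, and effort directed at the wrong step.

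**Working it through.** Part 1a states no sample size, effect size or model output, so there is no plan figure to reproduce. The check has a textual part and an illustrative part.

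**1. What the text fixes and what it leaves open**

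| Item | Status in the protocol |
|---|---|
| Full adjustment for all models | Stated, section 7 |
| Demographics, situational factors, patient outcomes as covariates for ordering | Stated as classes, section 7 |
| Prescribing place and time in the model | Not stated; the evident situational measures in 6.3 besides arrival time |
| NEWS and drug type in the model | Not stated; inferred from the extraction list |
| Total or conditional association as the target | Not stated |

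**2. Size, in closed form.** All inputs are assumptions. Let the later step be ward rather than ED prescribing and the upstream factor be out-of-hours arrival. Assume 55% sampled for in-hours ED prescribing and a direct odds ratio (OR) of 0.90 for out-of-hours arrival. With ward share w, the rate in each arrival group is (1 − w) × P(ED) + w × P(ward). The total OR compares the two rates.

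Example with ward OR 0.5. In-hours odds in ED are 0.55/0.45 = 1.222.
- In-hours: ED 0.550; ward 0.611/1.611 = 0.379.
- Out-of-hours: ED 1.100/2.100 = 0.524; ward 0.550/1.550 = 0.355.
- Ward share 20% in hours: 0.8 × 0.550 + 0.2 × 0.379 = 51.6%.
- Ward share 35% out of hours: 0.65 × 0.524 + 0.35 × 0.355 = 46.5%.
- Total OR = (0.465/0.535)/(0.516/0.484) = 0.81, against 0.90 adjusted.

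The same formula with other inputs:

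| Pathway | Ward share, in-hours v out-of-hours | Ward OR | Sampled, in-hours v out-of-hours | Total OR | Adjusted OR |
|---|---|---|---|---|---|
| Same direction | 20% v 35% | 0.5 | 51.6% v 46.5% | 0.81 | 0.90 |
| Same direction | 20% v 50% | 0.3 | 49.4% v 38.6% | 0.64 | 0.90 |
| None | 20% v 20% | 0.5 | 51.6% v 49.0% | 0.90 | 0.90 |
| Opposing | 35% v 20% | 0.5 | 49.0% v 49.0% | 1.00 | 0.90 |
| Opposing | 50% v 20% | 0.3 | 40.9% v 46.9% | 1.27 | 0.90 |

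**3. Simulation, 400,000 records per scenario, direct log-OR −0.3 (OR 0.74), about half sampled.**
- Same-direction pathway (factor to later step, log-OR −0.3 to −1.0; later step to sampling, 0.5 to 1.5): OR without the later step 0.72 to 0.54, with it about 0.74. The share of the log-OR removed runs from 1 − ln 0.741/ln 0.717 = 10% to 1 − ln 0.744/ln 0.543 = 52%.
- Opposing pathway through severity (factor raises severity by 0.2 to 0.4 SD, severity raises sampling): 0.79 to 1.09 without severity, about 0.74 with it. Adjustment makes the association look stronger.
- No pathway, strong later step: 0.765 without and 0.739 with. This shift is non-collapsibility of the OR, not mediation.
- Unmeasured common cause of later step and sampling: adjusted OR 0.78 to 0.84 against a true direct 0.74. The conditional estimate can itself be biased.

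**The case against.** The strongest objection is that the protocol nowhere says that NEWS, prescribing place, prescribing time and drug all enter one model. Section 6.3 is an extraction list. It also holds microbiology results and changes to antibiotics, which serve other objectives, so being listed does not make a measure a covariate. Covariate sets are usually left to the statistical analysis plan. This stands as a limit on the point: entry of NEWS and drug type is inference, and prescribing place and time are only the likeliest members of a named class. It does not remove the point, because full adjustment of all models and the patient-outcomes class are stated rules, and a plan consistent with section 7 would carry them over.

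A reader might infer that full adjustment hides the effect of ethnicity, deprivation or out-of-hours arrival. The documents do not support that. They give no path strengths or directions, and the calculations show the estimate can shrink, stay or grow.

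The aim can also be read as prediction, since section 6.3 speaks of predictors and section 7 of association, and mutual adjustment is ordinary there. Inequalities appear as patient feedback, not as a Part 1a objective. That is fair, and is why the full model should be kept rather than dropped.

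Finally, severity may confound arrival time, if sicker patients arrive at different hours, and whether a gap should be adjusted for clinical need is a choice of target, not an error. Both are right. A single model for arrival time without NEWS or diagnosis would risk confounding by case mix, so results with and without them are needed. The promised sensitivity analyses are unnamed and do not say from which model each factor is read.

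**Conclusion.** The point holds as one of clarity and interpretation. Section 7 applies one adjustment rule to factors at different stages and names a covariate class that follows the outcome. If the classes enter together, the odds ratios for ethnicity, deprivation, gender and arrival time are associations given later steps and should not be read as the overall gap in sampling.

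Neither the size nor the direction of the difference can be fixed from the documents. The same-direction figures (total OR 0.64 to 0.81 against 0.90; 10% to 52% of the log-OR removed) show what is possible, not what is expected. With an opposing pathway the adjusted association is the stronger one.

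The conclusion rests on two assumptions: that prescribing place and time are among the situational covariates, and that the overall gap is of interest. The objection to patient outcomes as covariates for ordering needs neither. The change is worth making because it is cheap and uses measures already listed for extraction.

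**What to change.** In Part 1a section 7:

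- (a) Remove patient outcomes as covariates for whether a culture is ordered.
- (b) Report the ethnicity, gender and deprivation gaps from a model with demographics and hospital only. Then add NEWS and admission diagnosis, to show the gap given clinical need.
- (c) Report arrival time from models with demographics and hospital, with and without NEWS and admission diagnosis, and without prescribing place, time or drug.
- (d) Use the fully adjusted model to interpret the prescribing variables. Show it for the other factors only as an association given the later steps.
- (e) Give marginal risk differences beside the odds ratios when comparing models, because odds ratios move between nested logistic models even without a pathway.

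The cost is a short paragraph in section 7, a few more model runs and longer results tables. No new data are needed.

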	3 DATA PROCESSING	
	ACCESS TO DATA	
9	MONITORING, AUDIT & INSPECTION	.13
10	ETHICAL AND REGULATORY CONSIDERATIONS	.13
10.1 10.2		
10.2		
10.0		

10.4	PROTOCOL COMPLIANCE AND SERIOUS BREACHES	15
10.5	DATA PROTECTION AND DATA SUBJECT CONFIDENTIALITY	15
10.6	INDEMNITY	15
10.7	ACCESS TO THE FINAL PROJECT DATASET	15
11 DI	SSEMINATION POLICY	16
12. REFE	RENCES	17

LIST OF ABBREVIATIONS

CI	Chief Investigator
GCP	Good Clinical Practice
NHS R&D	National Health Service Research & Development
PI	Principal Investigator
PIC	Participant Identification Centre
PIS	Participant Information Sheet
REC	Research Ethics Committee
SOP	Standard Operating Procedure

PROJECT SUMMARY

Project Title	Getting the bloods to the labora to improve the blood culture pa antimicrobial stewardship.	atory: developing interventions athway for patient safety and
Project Design	Cross-sectional study involving	analysis of routine NHS data
Planned Sample Size	No sample size was calculated all eligible participants	as data will be extracted for
Follow up duration	At time of extraction data will be extracted for the previous 12 months	
Planned Project Period	Jan 2023- June 2025	
	Objectives	Outcome Measures
Primary	To identify rate of occurrence and situational factors that affect whether blood culture sampling occurs, when broad-spectrum antibiotics for intravenous administration are prescribed within 24 hours of patient admission from emergency departments (ED).	% of participants where a blood culture sample was ordered
Secondary	To identify factors impacting on quality indicators e.g., number of sets, contamination, time to microbiology lab analyser; whether blood culture sampling occurs prior to administration of antibiotic. To conduct a secondary analysis to assess extent to which availability of blood samples was associated with changes to antibiotic choice at antibiotic review.	Adjusted odds ratios from logistic regression models

FUNDING AND SUPPORT IN KIND

FUNDER(S) (Names and contact details of ALL organisations providing funding and/or support in kind for this project)	FINANCIAL AND NON FINANCIALSUPPORT GIVEN
National Institute for Health Research (NIHR156452)	Financial support (£752,059.85)

ROLE OF PROJECT SPONSOR

The sponsor of this research is the University of Leicester. The University of Leicester is registered as a research sponsor with the Department of Health and routinely takes responsibility as sponsor for research activities within the NHS.

DATA FLOW DIAGRAM

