4 STUDY DESIGN

Study design: Cross-sectional study involving analysis of routine NHS data

Combined Protocol V3.0 22/07/24

Sample: All patients >18 years admitted to each trust, receiving broad-spectrum antibiotics for intravenous administration within 24 hours of admission, over a retrospective 12 month period (e.g. March 2023-February 2024).

Data sources: One hospital, with the main ED, will be selected from each trust. Data will be extracted from hospital electronic health records and electronic microbiology records. We will develop a standard schedule detailing the data points required and providing definitions. This will be discussed with the informatics team in each site to ensure comparable data can be provided. A data-sharing agreement will be established with each site.

Data will be fully anonymised within the trusts prior to transfer, by the nominated member of staff in the trust responsible for extracting and compiling the data. Identifying information e.g. date of birth and postcode will be substituted with higher level information e.g. age and Super Output Area. Primary data will be provided, trusts will Zip and encrypt data using 7-Zip software, and transfer using the University's secure Filedrop facility - https://filedrop.le.ac.uk/

We will incorporate internal checks of data-completeness (e.g. instances of patients with a blood culture result but no data on the time sample was ordered). Blood culture order time may not correlate with collection time. We will conduct a prospective data quality check, involving the use of stickers or audit forms to capture a manual record of actual blood culture sampling time. This will be checked against blood sample order time, and time of first dose of antibiotic, to assess the alignment between order time and collection time, and whether collection time precedes antibiotic administration, as a validation check of our use of blood culture sample order time as the primary outcome measure of blood culture sampling. Anonymised audit data will be transferred to the University of Leicester for and compiled for cross-site analysis.

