5 INCLUSION/EXCLUSION CRITERIA

5.1 Inclusion criteria

- adults (>18 years)
- admitted to hospital through emergency routes between 01/03/2023 and 29/02/2024
- prescribed broad-spectrum antibiotics for intravenous administration within 24 hours of admission

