8.1.1 DATASET CREATION

The study statistician will develop a standard schedule detailing the data points required and providing definitions. This will be discussed with the informatics team in each site to ensure comparable data can be provided. A data-sharing agreement will be established with each site. Data will be fully anonymised within the trusts prior to transfer, by the nominated member of staff in the trust responsible for extracting and compiling the data. Identifying information e.g. date of birth and postcode will be substituted with higher level information e.g. age and Super Output Area. Data will include local patient identifier numbers (a unique identifier for a patient within a health care provider); patients cannot be identified by these numbers once data are transferred

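### All Part 1a models are committed to a mixed-effects hospital term with only three hospitals; hospital should be a fixed factor, and the handling of repeat admissions should be stated

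*Protocol*

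**What the plan says.** Section 7 (Statistics and data analysis) plans logistic regression for blood culture ordering, logistic or linear regression for the quality indicators, and logistic regression for antibiotic change at review. It then says that all models "will be mixed effects to account for the clustering effect of hospital, as data is being drawn from three sites". Hospital is the only clustering level named. Sensitivity analyses to other model specifications are promised in general terms, without naming a fixed-effect model or a small-sample correction.

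Section 4 settles the number of hospitals: "One hospital, with the main ED, will be selected from each trust". Section 6.3 confirms three participating hospitals. Section 5.2.2 of the Part 1c and Part 2 protocol, in the same combined document, says the three trusts were picked for diversity.

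The Project Summary says "No sample size was calculated" because all eligible records are taken. The data run "over a retrospective 12 month period", and Section 5.1 admits adults "admitted to hospital through emergency routes between 01/03/2023 and 29/02/2024". Section 8.1.1 adds that "Data will include local patient identifier numbers (a unique identifier for a patient within a health care provider". The primary objective (Section 3.1) is "To identify rate of occurrence and situational factors that affect whether blood culture sampling occurs".

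**The concern.** A random hospital effect treats the hospitals as draws from a population and learns its spread from them. Three hospitals say almost nothing about that spread, and these three were not drawn at random. The variance estimate controls how strongly the model adjusts for site. If it comes out at zero, the model becomes a regression with no hospital term, and a covariate whose mix differs between sites picks up the site differences. That matters most where events are few and the data cannot correct it. The same variance drives the interval for any overall rate read from the model and for any hospital-level factor.

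A second source of dependence may exist. Eligibility and outcome are both defined relative to an admission, so one person could qualify more than once in a year. The plan does not say whether the row is a patient or an admission.

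**Working it through.** Part 1a gives no sample size, power, or intraclass correlation (ICC), so there is no stated figure to reproduce.

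**1. Precision of the hospital variance.** Input: 3 hospitals (Sections 4 and 6.3), so 2 df.
- The 95% limits for the variance, as multiples of its estimate, are 2/χ²(0.975; 2 df) = 0.271 and 2/χ²(0.025; 2 df) = 39.5.
- Taking square roots, the SD limits are 0.52 and 6.28 times the estimate.

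**2. A model-based overall rate.** A nominal 95% Wald interval for the intercept has the following coverage.
- With REML scaling: P(|t₂| < 1.96) = 0.81.
- With ML scaling: P(|t₂| < 1.96·√(2/3)) = 0.75.
- A simulation of a random-intercept logistic model agrees. It had 3 hospitals, 1000 or 3000 patients per site, hospital SD 0.3 or 0.6 on the logit scale, a baseline rate near one half, and 400 runs per setting. Coverage was 73–79%, and the estimated SD fell below half its true value in 28–37% of runs.

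Site sizes and hospital SDs are assumptions. The baseline rate follows the Background section.

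**3. Patient-level covariates, common outcome.** In the same simulation, the mean standard errors were:

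| Patients per site | Hospital SD | Mixed | Fixed |
|---|---|---|---|
| 1000 | 0.3 | 0.0760 | 0.0760 |
| 1000 | 0.6 | 0.0785 | 0.0785 |
| 3000 | 0.3 | 0.0438 | 0.0438 |
| 3000 | 0.6 | 0.0451 | 0.0451 |

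Coverage was 93–97% under both models. The covariate mix was the same at every site here, so this tests the standard errors and not confounding by site.

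**4. Few events, covariate mix differing by site.** A second simulation assumed a binary indicator at about 4%, 500–1500 records per site, and a covariate distributed differently across sites.
- The random-intercept variance collapsed to zero in 11–53% of runs.
- The log odds ratio kept a bias of 0.07–0.20, which is a factor of e^0.07 = 1.07 to e^0.20 = 1.22 on the odds ratio.
- Coverage was 88–89%, against 94–95% with hospital as a fixed factor.
- For a common outcome with large sites the bias was negligible.

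These values depend on the assumed site differences.

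**5. Repeat admissions, only if admissions are the rows.** For a covariate constant within patient, the design effect is 1 + (E[m²]/E[m] − 1) × ICC, where m is admissions per patient. Assumptions: 5–30% of patients are readmitted (70% of them with two admissions, 30% with three), and the within-patient ICC is 0.05–0.5.
- 5% readmitted: E[m] = 0.95 + 0.07 + 0.045 = 1.065 and E[m²] = 0.95 + 0.14 + 0.135 = 1.225, so the bracket is 0.150. The design effect is 1.008–1.075 and the SE multiplier (its square root) is 1.004–1.037.
- 30% readmitted: E[m] = 0.70 + 0.42 + 0.27 = 1.39 and E[m²] = 0.70 + 0.84 + 0.81 = 2.35, so the bracket is 0.691. The design effect is 1.035–1.345 and the SE multiplier is 1.017–1.160.

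Across this range the nominal 5% type I error becomes 5.1–9.1%.

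**The case against.** The strongest reply is that the hospital variance is a nuisance parameter that no objective asks for, and that the outputs people will read are barely touched. Much of this stands. A reader might infer that all standard errors in Part 1a are too small; step 3 shows otherwise for patient-level covariates of a common outcome, and the measures listed in Section 6.3 are recorded per patient or admission. A reader might also infer that the primary rate carries the poor coverage of step 2. The Project Summary defines that outcome as a percentage of participants, and Section 7 summarises ordering descriptively, so step 2 applies only if a rate is taken from the model.

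It is also tempting to say that the plan ignores repeat admissions. That is not established. The eligibility wording is per person, the dataset carries "a unique identifier for a patient within a health care provider", and Section 6.2 refers to a Statistical Analysis Plan that is not available here and may fix the index admission. The figures in step 5 rest on assumed inputs, and covariates that change between admissions would generally show less inflation.

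What the reply does not answer is step 4. The quality indicators include contamination, which may be rare, and Section 7 applies the same hospital term to every model. The general promise of sensitivity analyses names no fixed-effect model and does not undo an explicit commitment for the main analyses.

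**Conclusion.** The point holds for the hospital term. The protocol itself fixes a specification whose variance three hospitals cannot estimate: the SD is known only to within about 0.5 to 6.3 times its estimate, a result that needs no assumption beyond normal-theory limits on 2 df. The practical harm is residual confounding by site in models with few events, plus unreliable inference for a model-based overall rate or a hospital-level factor. The size of the confounding rests on assumed event rates, site sizes and site differences. For patient-level odds ratios of common outcomes at large sites, the choice makes little difference.

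The repeat-admission point is secondary and conditional. It matters only if admissions are analysed as independent rows, and its size cannot be derived from the documents. Under the assumptions in step 5, correct standard errors would be roughly 0–16% larger than those reported.

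**What to change.** In Section 7, replace the mixed-effects sentence so that hospital enters every Part 1a model as a fixed factor with two indicators. Report the blood culture rate for each hospital beside the pooled rate, and state that conclusions are limited to these three sites.

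State the unit of analysis. If admissions are the rows, use patient-clustered robust standard errors based on the local identifier in Section 8.1.1, and add a sensitivity analysis restricted to each patient's first eligible admission. That identifier links repeats only within one provider.

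The cost is a few sentences and two parameters per model; step 3 shows no loss of precision for patient-level covariates. The downside is that nothing can be inferred about other hospitals, and hospital-level factors (for example in-house against outsourced laboratory services) cannot be separated from hospital itself. Three sites could not support either in any case.
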